E2.4.1 Statistical power and sample size considerations: As we view tertiary analyses as exploratory and hypothesis generating, we do not present a priori specified sample size or minimum detectable effect size statistics. We have no doubt that we may be underpowered to detect all but large moderation effects. Our inferences will be made cautiously and be guided

by confidence intervals obtained by bootstrap resampling of the observed data.

E3. Aim 2 Analytical Plan (Analyses Related to Cognition and Neuroimaging)

All de-identified data from this study for Aim 2 will be combined with data from subjects who completed neuroimaging procedures in PVAMC IRB protocol #2018-051.

E3.1 Evaluate the relationship between STBs and reward circuits involved in decision-making in Veterans.

Hypothesis: Neural and behavioral correlates of decision-making will differentiate Veterans with STBs from those without STBs.

Rationale: Suicidality is associated with maladaptive decision-making. Neuroimaging in non-Veterans has shown that STBs are accompanied by functional and anatomical differences in the striatal-to-VMPFC reward circuit implicated in decision-making. It is unknown if these potential neurocognitive markers of suicide generalize to Veterans.

Between-group contrasts of decision-making, structural MRI, and functional MRI will be used to test our hypothesis.

E5.1 Participant groups: The STB group will be comprised of Veterans hospitalized for suicide attempt (up to n=30) or suicidal ideation (up to n=30). The diagnosis matched control group is comprised of Veterans (up to n=60) without current STBs. Per power estimations computed with G Power software⁴², 85% power to detect a medium-sized effect of group (0.4) in an ANCOVA model with three groups and two covariates is afforded by a total sample size of 72, or n=24 participants per group. Our enrollment targets exceed this estimate to account for loss of participants that are unable to complete all aspects of the study.

Data sources: Decision-making tasks include the scanned reward expectancy task (card guessing), and the un-scanned Iowa Gambling and Monetary Choice (Delay Discounting) tasks. Structural MRI and diffusion MRI data. FMRI data used in Aim 1 analyses will come from either the card guessing reward task or resting state functional MRI runs.

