General statistical details: Age and sex will be treated as covariates of no interest in all statistical analyses. Intracranial volume (computed by Freesurfer) will also be used as a nuisance covariate in morphometry analyses to control for size-related variance. Residual effects of motion on functional connectivity estimates will be tested post hoc by regressing individuals' frame-to- frame motion against

functional connectivity beta values ⁵⁵. Potential effects of impulsivity, depression, anxiety, and sleep on outcomes will be explored in post hoc sensitivity analyses.

Behavioral Data Analysis:

PhenX Toolbox Monetary-Choice Questionnaire⁴³: The protocol is scored by calculating where the respondent's answers place him or her amid reference discounting curves; placement amid steeper curves indicates higher levels of impulsivity. Subject-specific discounting rates will be entered into MATLAB ANCOVA models testing group differences.

PhenX Toolbox The Iowa Gambling Test^{TM 4}: Total winnings and the ratio of high vs. low risk gambles will be entered into MATLAB ANCOVA models testing group differences.

MRI Analyses: Analyses for primary hypothesis testing will employ a region of interest (ROI) approach. ROIs in VMPFC, orbitofrontal cortex, and the striatum will be used in structural and functional neuroimaging analyses. Cortical ROI definitions will be based on the Human Connectome Project multi-modal parcellation atlas [81]; subcortical ROIs will be based on Freesurfer automated parcellations. ROI analyses will be considered significant at the two-tailed alpha of $p < .05$ after Bonferroni-correction for the number of ROI comparisons. We may also conduct exploratory voxel-level fMRI analyses. These analyses will be corrected for multiple comparisons by applying a voxel-height threshold of $p < .001$, and a cluster-size threshold of $p - \text{FDR} < .05$ to all second-level models.

Grey matter comparisons between Veterans exhibiting STBs and matched controls.

Cortical thickness and grey matter volume (as computed by Freesurfer) will be extracted from the VMPFC and striatum. Measures will be compared between Veterans with STBs and matched controls to test the hypothesis that these metrics are reduced in Veterans with STBs.

Differences in white matter integrity between Veterans with STBs and controls.

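### The ROI tests in E3.1 and E3.2 use plain Bonferroni; Holm's step-down rule keeps the same 5% family-wise bound and detects more regions when several differ (cheap improvement)

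*Combined protocol and SAP*

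**What the plan says.** The MRI Analyses paragraph of E3.1 states: "Analyses for primary hypothesis testing will employ a region of interest (ROI) approach". It then sets the rule: "ROI analyses will be considered significant at the two-tailed alpha of $p < .05$ after Bonferroni-correction for the number of ROI comparisons". The MRI Analyses paragraph of E3.2 repeats that rule, again "after Bonferroni-correction for the number of ROI comparisons". Neither section mentions a stepwise method.

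E3.1 names three regions: "ROIs in VMPFC, orbitofrontal cortex, and the striatum will be used in structural and functional neuroimaging analyses". E3.2 names three parts of ventrolateral PFC, dorsolateral PFC, two parts of the anterior cingulate, and striatal ROIs. That makes seven if the striatum counts once. Neither section says how many parcels, hemispheres, modalities or contrasts make up the number of comparisons.

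The groups are given in the Participant groups paragraph of E3.1: "suicide attempt (up to n=30) or suicidal ideation (up to n=30" each for the suicidal Veterans, and up to 60 controls. The only power statement for these groups is "85% power to detect a medium-sized effect of group (0.4") "in an ANCOVA model with three groups and two covariates", reached with "a total sample size of 72, or n=24 participants per group". It does not mention the multiplicity correction.

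**The concern.** These ROI tests decide the Aim 2 biomarker hypotheses; they do not affect the treatment comparison. Bonferroni holds every ROI to .05/m, where m is the number of comparisons. Holm applies .05/m only to the smallest p-value and relaxes the threshold after each rejection. It needs no assumption about correlation, no extra data and no extra participants.

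The plan often predicts more than one affected region: VMPFC and striatum in E3.1, and cognitive control regions as a set in E3.2. In that situation Bonferroni can leave a second or third true difference undeclared that Holm would declare at the same nominal error rate.

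**Working it through.** **1. The plan's own figure.** Take a three-group ANCOVA with two covariates, N = 72, f = 0.4, and alpha = 0.05 (assumed, since it is not stated). Then df1 = 2, df2 = 72 − 3 − 2 = 67, and noncentrality = f² × N = 0.16 × 72 = 11.52. Power is 0.853, so the stated 85% reproduces at unadjusted alpha. At .05/m, power per ROI is 0.724 for m = 3 and 0.633 for m = 6. At N = 120 it is 0.944 and 0.909.

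**2. Why Holm never rejects less.** Order the p-values and reject the j-th while p(j) ≤ .05/(m − j + 1). For m = 3 the thresholds are .0167, .025 and .05. Every threshold is at least .05/m, so anything Bonferroni rejects, Holm rejects.

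**3. Why the bound is the same.** With m0 true nulls, the first true null to be rejected is met at step m − m0 + 1 at the latest, where the threshold is .05/m0. The chance that any of the m0 nulls falls below that is at most m0 × .05/m0 = .05, whatever the correlation.

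**4. Bonferroni power per ROI, two-group t-test.** Noncentrality = d × √(n/2), df = 2n − 2, two-sided alpha .05/m.
- 60 v 60, d = 0.5, m = 3: 0.5 × √30 = 2.739, critical t 2.429, power 62.2%.
- 30 v 30, d = 0.8, m = 7: 0.8 × √15 = 3.098, critical t 2.789, power 62.2%.
- 30 v 30, d = 0.5, m = 7: 0.5 × √15 = 1.936, critical t 2.789, power 20.8%.

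**5. Bonferroni v Holm by simulation.** 20,000 runs per row, ROI correlation 0.4. The values of d, m, the correlation and the number of affected ROIs are assumptions, because the documents give none of them for these tests.

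| Setting | Affected | Average power per affected ROI | At least one affected ROI found |
|---|---|---|---|
| 60 v 60, d = 0.5, m = 3 | 1 | 62.5% v 62.6% | 62.5% v 62.6% |
| | 2 | 62.4% v 65.9% | 79.8% v 79.9% |
| | 3 | 62.1% v 70.3% | 87.2% v 87.2% |
| 30 v 30, d = 0.8, m = 7 | 1 | 61.7% v 61.7% | 61.7% v 61.7% |
| | 4 | 62.1% v 66.4% | 91.1% v 91.2% |
| | 7 | 62.5% v 74.5% | 96.0% v 96.0% |
| 30 v 30, d = 0.5, m = 7 | 1 | 20.6% v 20.7% | 20.6% v 20.7% |
| | 4 | 20.8% v 22.4% | 48.9% v 48.9% |
| | 7 | 20.5% v 25.0% | 61.7% v 61.7% |

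Other seeds moved these figures by about a point. In no run did Bonferroni reject an ROI that Holm did not.

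**6. Realised family-wise error, Bonferroni v Holm.** With 2 of 3 affected: 1.5% v 3.4%. With 4 of 7 affected (d = 0.8): 2.2% v 3.7%. All are below 5%.

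**7. Same comparison in the plan's ANCOVA setting.** With f = 0.4, N = 72, m = 3 and correlation 0 or 0.5, average power per affected ROI goes from 0.72 to 0.72 with one affected, from 0.72–0.73 to 0.76 with two, and from 0.72–0.73 to 0.80–0.82 with three.

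**The case against.** Bonferroni is prespecified, valid and stated the same way in both sections, so there is no error or contradiction to correct. That stands, and it limits this point to efficiency.

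The E3.1 hypothesis is that neural and behavioral correlates separate the groups; it does not need every region to differ. Holm's first threshold is also .05/m, so the chance of any positive finding does not improve. That stands too. In addition, not every test expects several regions to differ: the inhibition fMRI contrast in E3.2 anticipates a difference in VLPFC specifically, and with one affected region the gain is nil.

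Bonferroni's realised family-wise error is lower when some regions are null (step 6), so the switch gives up some unclaimed conservatism. The promised 5% bound is unaffected.

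The group sizes may be understated, because E3 says the data will be combined with another imaging protocol (#2018-051). This would change the size of the gain, but not its direction.

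Three stronger readings are tempting, and the documents do not support them:
- A reader might infer that the loss is peculiar to small samples. It depends on m, on how many regions differ and on the power level. With three affected ROIs at f = 0.25, the gain is larger at N = 120 (0.51 to 0.59) than at N = 72 (0.27–0.28 to 0.32).
- A reader might cite the chance of finding all seven E3.2 regions, about 17% v 48%. That requires all seven to differ by 0.8 SD and success to mean finding every one; the plan states neither.
- A reader might expect Holm to restore the stated 85% power. At N = 72 and m = 3 it reaches at most about 0.82 on average, and only when all three regions differ.

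**Conclusion.** The point holds as a minor efficiency improvement. At the same 5% family-wise level and under any dependence, Holm is never worse than Bonferroni in what it rejects, and it is better when two or more regions differ.

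Under the assumed settings the gain in average power per affected ROI is about 3 to 4 points with 2 of 3 affected and about 8 points with 3 of 3 (60 v 60, d = 0.5). For 7 ROIs at 30 v 30 with d = 0.8 it is about 4 to 5 points with 4 of 7 affected and about 12 points with 7 of 7. With d = 0.5 at 30 v 30 it is only about 2 to 4 points. It is zero with one affected region, and the chance of at least one detection is essentially unchanged throughout.

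That Holm never rejects less, and that the error bound is the same, are mathematical facts. The sizes rest on the assumed m, effect size, correlation and number of affected regions.

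**What to change.** In the MRI Analyses paragraphs of E3.1 and E3.2, replace the correction wording ("after Bonferroni-correction for the number of ROI comparisons") with: *after Holm step-down correction (family-wise alpha .05, two-tailed) over the ROI comparisons*. In the same place, list the comparisons that form each family: parcels, hemispheres, modalities and group contrasts. Either method needs that list, because m is otherwise open.

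The cost is a wording change, made before the imaging outcomes are analysed. Holm has no simple simultaneous confidence intervals, so report intervals at the Bonferroni level. Realised family-wise error will be slightly higher than under Bonferroni, but still at most 5%.

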Deterministic tractography of diffusion data will be conducted with DSI Studio (<http://dsi-studio.labsolver.org/>). The generalized q-sampling algorithm will be used for fiber reconstruction. This algorithm permits estimation of multiple fibers per voxel improving reconstruction accuracy in areas rich in crossing fibers [82]. Fiber streamlines will be estimated from "seed" ROIs and then filtered to exclude streamlines passing through, but not ending in, target ROIs. If the seed is in striatum, targets will be located in VMPFC/orbitofrontal cortex, or vice versa. To test the hypothesis that white matter pathways connecting VMPFC-to-striatum are compromised in Veterans with STBs, individual-level track statistics (anisotropy, density) will be entered into MATLAB ANCOVA models.

Differences in fMRI activation during decision-making between Veterans with/out STBs.

These analyses test the hypothesis that neural signals in the striatal-to-VMPFC circuit related to rewards and decision-making are attenuated in Veterans with STBs. Preprocessed fMRI data from the reward expectancy task will be used for these analyses. Whole-brain first-level fixed-effect GLMs will be constructed for each subject with SPM12. A parametric regressor will be used to model univariate fMRI activation related to reward expectancy.

Parametric values are set to +0.5 for probable wins, -0.375 for probable losses, +0.125 for ambiguous cues, and zero for the neutral cues (see D5.5.2) [83]. Separate regressors for positive (better than expected) and negative (worse than expected) prediction errors will also be constructed. GLMs will be created by convolving the canonical hemodynamic response function with regressors of interest and nuisance regressors (motion parameters and derivatives, mean signal in cerebrospinal fluid). Subjects will be treated as random effects in second-level univariate fMRI models. To evaluate whether reward-related signals are blunted in Veteran with STBs, the averaged blood oxygen level-dependent (BOLD) signal for our conditions of interest will be extracted from VMPFC and striatal ROIs and contrasted between groups. Whole-brain statistical maps for reward expectancy and prediction errors will also be contrasted between Veterans with STBs and controls.

Statistically significant clusters from this univariate whole-brain analysis may be used as ROIs in functional connectivity models below.

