Differences in functional connectivity between Veterans with STBs and controls.

These analyses test the hypothesis that the VMPFC-to-striatal decision-making circuit is less functionally cohesive in Veterans with STBs. Functional connectivity analyses of both task (reward expectancy) and resting-state will be conducted using the CONN Toolbox.⁵⁰

Unsmoothed residual BOLD time courses will be extracted from each subjects' preprocessed data and then cross-correlated. The resulting correlations will be converted to z-scores via Fisher's R-to-Z transformation in order to improve conformation to the assumptions of the GLMs used for seed-based hypothesis testing. Z-scores will be entered into GLMs comparing VMPFC-to-striatal connectivity between groups. For task-based functional connectivity, a weighted GLM approach will be used to compare connectivity during the expected reward and prediction error task conditions of between Veterans with and without STBs. Additional analyses using ROIs functionally-defined in the univariate analysis described above as seeds may also be run.

Design Considerations & Alternative Outcomes: This hypothesis testing sequence focuses on the VMPFC-to-striatum decision-making circuit. However, effects may be mediated by regions outside this *a priori* network e.g. in the amygdala-to-VMPFC circuit implicated in bipolar disorder with suicidality [85]. The role of this circuit could be explored should we fail to reject the null hypothesis. Alternatively, a data-driven method such as multi-voxel pattern analysis could be used to functionally identify neural circuits differing between Veterans with and without STBs.

E3.2 Evaluate whether correlates of decision-making and cognitive control indicate risk severity.

Hypotheses: Decision-making will be less risky and/or impulsive in higher- vs. lower- risk Veterans with STBs. Structural and functional integrity of cognitive control regions will be superior in higher-risk Veterans with STBs.

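### Optional connectivity tests may take their seeds from clusters that already differ between Veterans with STBs and controls, with no safeguard for independence

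*Combined protocol and SAP*

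**What the plan says.** In E3.1, under the heading on fMRI activation during decision-making, the activation analysis uses the reward expectancy task: "Preprocessed fMRI data from the reward expectancy task will be used for these analyses". After the ROI contrasts the plan adds a voxel-level comparison: "Whole-brain statistical maps for reward expectancy and prediction errors will also be contrasted between Veterans with STBs and controls". The next sentence permits reuse: "Statistically significant clusters from this univariate whole-brain analysis may be used as ROIs in functional connectivity models below".

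The following heading, on group differences in functional connectivity, takes up that permission: "Additional analyses using ROIs functionally-defined in the univariate analysis described above as seeds may also be run". Both kinds of run are covered: "Functional connectivity analyses of both task (reward expectancy) and resting-state will be conducted using the CONN Toolbox". For task runs, "a weighted GLM approach will be used to compare connectivity during the expected reward and prediction error task conditions", again between Veterans with and without STBs.

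The main connectivity test is set in advance: "Z-scores will be entered into GLMs comparing VMPFC-to-striatal connectivity between groups". Its regions do not come from the group map: "Cortical ROI definitions will be based on the Human Connectome Project multi-modal parcellation atlas", with subcortical regions from automated parcellation. ROI tests use two-tailed .05 with Bonferroni correction. Exploratory voxel-level maps use a voxel height of p < .001 plus a cluster-size FDR threshold.

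E3.4.5 lists what is removed before connectivity is computed: white-matter and CSF components, linear trend, motion parameters with derivatives, and flagged volumes. Task-condition regressors are not on the list. E3.1 mentions no split sample, independent localizer, cross-validation, or permutation that repeats the selection.

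**The concern.** A cluster that passes the STB-control activation contrast is, by selection, a place where the sample groups differ. If part of that difference is chance, and if a person's activation there is related to the connectivity of the same region, the chance difference carries into the connectivity test. The nominal 5% level then no longer holds for that seed.

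Task runs offer a plain route for this. If the evoked response stays in the time courses, people with larger responses will tend to show larger seed-to-target correlations, because both regions follow the same task signal.

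At stake is how the second result is read. Identifying brain-based biomarkers of suicidality is one of the study's two objectives (section A). An activation cluster followed by a connectivity difference seeded from it could be taken for two separate findings when the second is partly inherited from the first. Because reuse is optional, the seeds can also be chosen after the group map has been seen.

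**Working it through.** **1. The plan's own figure.** The only sample-size statement for these contrasts (participant groups, E3.1) is N = 72 for 85% power at f = 0.4, with three groups and two covariates. With lambda = f² × N = 0.16 × 72 = 11.52, degrees of freedom 2 and 72 − 5 = 67, and alpha .05 (assumed; not stated beside the figure), power is 0.853, and 72 is the smallest N that reaches 85%. It reproduces. Nothing below depends on it. The plan gives no error rate for seed-based tests beyond the general ROI alpha.

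**2. Selection and test side by side.**

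| | Selection | Task connectivity test | Resting connectivity test |
|---|---|---|---|
| Groups | STB v control | STB v control | STB v control |
| People | same | same | same |
| Runs (Table 4) | reward task, runs 5-6 | reward task, runs 5-6 | rest, runs 3-4 |
| Quantity | activation amplitude | correlation of time courses | correlation of time courses |

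The factor and the people coincide throughout. The runs coincide only for task connectivity. The quantity never coincides, so any bias must come through a link between amplitude and connectivity.

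**3. Error rate given a chance-selected seed.** Let z_A and z_C be the group-difference statistics for activation and connectivity, both null, with correlation rho (the within-group correlation of a person's activation and connectivity values). Selection at two-sided p < .001 means |z_A| > 3.29; by symmetry take the positive side. Then

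- z_C given z_A is normal with mean rho × z_A and variance 1 − rho²;
- the mean of z_A after selection is phi(3.29)/.0005 = .00178/.0005 = 3.56.

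Hand check at rho = .3: mean 0.3 × 3.56 = 1.07, SD √(1 − .09) = .954, so the upper tail starts at (1.96 − 1.07)/.954 = 0.93, a probability of about .175. Drawing z_A from its full truncated distribution (400,000 draws) gives:

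| Assumed rho | Rejection rate of a nominal 5% test |
|---|---|
| 0 | 5.0% |
| .1 | 6.4% |
| .2 | 10.4% |
| .3 | 17.6% |
| .5 | 41.8% |
| .7 | 76.4% |

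The documents give no value for rho.

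**4. Time-series simulation of the mechanism.** Settings: 60 v 60 (the enrolment ceilings in E3.1), 480 volumes and 48 trials (one reward run), and no true group difference in activation or coupling. The seed is one of 300 voxels whose activation contrast reached p < .001 by chance. Response amplitudes, relative to unit noise, are assumptions.

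| Seed and data | Amplitude mean 0.3, SD 0.2 | Amplitude mean 0.5, SD 0.3 |
|---|---|---|
| Selected, task response kept | 41% | 52% |
| Selected, task response regressed out | 5.3% | 2.9% |
| Selected, separate resting run | 5.3% | 3.6% |
| Random seed, task response kept | 6.4% | 4.5% |

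The selected-seed rows rest on 375 and 384 replicates, so near 5% the Monte Carlo error is √(.05 × .95/375) = 1.1 points. The resting data were generated with no link to activation; where such a link exists, the table in step 3 applies. The simulation omits cluster-size FDR, the age and sex covariates and spatial correlation, and it correlates whole runs instead of weighting by condition. It shows direction and rough size only.

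**5. Conditional against joint rate.** These rates apply after a false cluster has been selected. If that happened in 5% of analyses with no true effect (an assumption), the joint rate of a false cluster followed by a false connectivity result at rho = .5 would be .05 × .418 = 2.1%.

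**The case against.** The case against is substantial, and most of it stands.

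- **Different quantities.** Amplitude selects and correlation is tested. A reader might infer a circular test that is bound to produce false positives. The documents do not support that: with rho = 0, or with task effects removed, the rate stays near 5%.
- **Rest is separate data.** Runs 3-4 are not used for selection, so bias there needs a correlation between task activation and resting connectivity across people.
- **Low rank in the plan.** A5 lists the baseline comparison with controls as exploratory, E3.1 calls voxel-level fMRI work exploratory, and seed reuse is additional and optional. A reader might infer that the main connectivity result is compromised. It is not, since its regions are fixed in advance. Nor does the plan say that seed-based results will be offered as confirmation of the activation finding; that is a risk of interpretation.
- **Antecedent.** The phrase that names the source analysis could also cover a map pooled over groups. The group contrast is the nearest and likelier referent, but not the only possible one.
- **Silence on task regressors.** E3.4.5 describes additional steps, and E3.1 speaks of residual time courses. Removal of task effects is unstated, not ruled out.
- **Magnitude.** A reader might take 42% for the study's error rate. It is conditional, and rho is assumed. Cluster-size FDR makes a chance cluster rarer, and Bonferroni correction, if applied to these seeds, would lower the rate further.

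What does not fall away is that neither correction addresses how a seed was chosen. Once a false cluster is in hand, the dependence remains. E3.1 attaches its exploratory label to the voxel-level maps and not to the seed tests themselves.

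**Conclusion.** The point holds in limited form. The plan allows a selection rule that can bias optional STB-control connectivity tests, and it states nothing that would prevent this. The exposure is mainly in task connectivity. Its size, given a chance-selected cluster, runs from no inflation (5%) at rho = 0 to about 10%, 18% and 42% at .2, .3 and .5. This rests on an assumed rho, a voxel-only selection threshold, no true group difference, and the group-contrast reading of the source map. Resting-state tests are exposed only if activation and resting connectivity are related across people. The treatment comparison and the atlas-based imaging tests are untouched. It is worth correcting because the change is cheap, not because the main conclusions depend on it.

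**What to change.** In E3.1, state that functionally defined seeds for group connectivity tests come either from a group-blind map (the main effect of reward expectancy or prediction error over all participants pooled) or from atlas regions. In E3.4.5, state that task-condition effects are regressed out of the reward-task time courses before connectivity is computed.

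If group-contrast clusters are still to be used as seeds, either permute group labels through selection and test together, or report the results as descriptive only and not as independent confirmation of the activation finding.

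The cost is a few sentences and slightly more analysis work, with no new data. The drawback is that group-blind or atlas seeds may miss the site of the largest group difference.
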